2.2.1 Clinical

In infants with seizures, phenobarbital 15–20 mg loading dose with additional 5–10 mg/kg doses to maximal plasma concentration of 40 mg/L (172 micromol/L) resulted in a plateau of the response rate. Plasma concentrations >50 mg/L (215 micromol/L) were associated with sedation and feeding difficulty (9).

The clearance of phenobarbital increases with birth weight and postnatal age, but is reduced at a concentration >50 mg/L (215 micromol/L) (10). Bioavailability is 50% after oral administration. Simulations recommend a loading dose 20 mg/kg and maintenance 2.5 – 5 mg/kg/day for intravenous administration and; loading dose 40 mg/kg and maintenance 5 – 11 mg/kg/day for oral administration to meet a target phenobarbital concentration between 15 and 30 mg/L (64.5 and 129.1 micromol/L) (11). The clinical management of neonatal seizures and the doses (both partial and cumulative) of phenobarbital administered as first line therapy have generally varied among clinicians and institutions. A total dose of 50 mg/kg can be given if required (12).

The clearance may also be reduced in infants with perinatal asphyxia undergoing therapeutic hypothermia (13-15). In term infants treated with hypothermia, an initial phenobarbital loading dose of 20 mg/kg with an additional 10–20 mg/kg if needed is recommended (15).

2.2.2 Importance of Clinical Trial

This clinical trial represents a national and international, therapeutic confirmatory study to further demonstrate the tolerability, safety and efficacy of phenobarbital use in neonatal seizures.

2.3 Risk/Benefit Assessment

2.3.1 Known Potential Risks

2.3.1.1 *Contraindications*

Hypersensitivity to phenobarbital or any ingredients. Any forms of acute porphyria.

2.3.1.2 *Precautions*

Use with caution in renal or hepatic impairment. Dependence may develop with prolonged use – consider weaning instead of abrupt withdrawal. Therapeutic hypothermia may increase the serum concentrations of phenobarbital – monitor serum concentrations closely.

Additional precautions in preterm infants, especially those with extreme immaturity and neonates with respiratory failure.

2.3.1.3 Drug Interactions

Phenobarbital is known as an inducer of microsomal liver enzymes. Morphine, fentanyl, midazolam and other CNS depressants may cause reduced blood levels when co-administered with phenobarbital, resulting in ineffective treatment (16-18). If phenobarbital is substituted by non-CYP3A inducers, lower doses of other drugs might be appropriate to avoid excessive exposure.

Acceleration of elimination of digoxin, metronidazole, corticosteroids (e.g. betamethasone, dexamethasone), vitamin D, and beta-blockers (e.g. propranolol, sotalol), resulting in reduced plasma levels may occur if administered concurrently with phenobarbital. Concurrent administration of phenytoin with phenobarbital has variable effects on serum concentrations of either drug. Serum concentrations should be monitored for both drugs.

2.3.1.4 Adverse Reactions

Expected phenobarbital adverse reactions include drowsiness, lethargy, impaired sucking reflex and poor feeding. If administration is too rapid, expected adverse reactions include respiratory depression, apnea, hypotension, laryngospasm and bronchospasm. Other expected adverse reactions include phlebitis, tissue necrosis if extravasation occurs, GI intolerance, physical dependence and tolerance, folate deficiency, hepatitis and hypocalcaemia.

Stevens-Johnson syndrome and Toxic Epidermal Necrolysis: Serious and sometimes fatal dermatologic reactions, including Stevens-Johnson syndrome (SJS) and Toxic Epidermal Necrolysis (TEN) have been reported with phenobarbital. Post-marketing reporting rate is generally accepted to be an underestimate due to under-reporting. Recurrence of serious skin reactions following re- challenge with phenobarbital has also been reported. Therefore, if a study participant develops a skin reaction during phenobarbital treatment, consideration should be given to permanent discontinuation and replacement of the drug with alternative treatment.

2.3.2 Known Potential Benefits

Phenobarbital has been recommended as first-line treatment for neonatal seizures (19). In RCTs, phenobarbital (target plasma concentration 25 mg/L) was reported to be similarly as effective as phenytoin (target plasma concentration 3 mg/L) for control of electrical seizures (43% versus 45%) (20); and phenobarbital 20 mg/kg was reported to be more effective than phenytoin 20 mg/kg at controlling clinical seizures (72% versus 15%) (21).

2.3.3 Assessment of Potential Risks and Benefits

Overall, this is a carefully designed trial targeting to meet its objectives of providing effective neonatal seizure treatment without exposing study participants to any unnecessary risk.

2.3.3.1 *Physical Harms*

The study is designed to measure the effects of therapeutic doses of phenobarbital for treating neonatal seizures. The risks associated with the drug is assumed not to be beyond those presented during standard of care treatment or described in the literature (12). The doses tested in this study are within the dosing guidelines available in the literature (12). The increased number of blood draws required for the study can be considered beyond that of standard of care. There is risk associated with multiple blood draws during a prespecified time period.

2.3.3.2 *Psychological Harms*

The risks associated with the drug are assumed not to be beyond those presented during standard of care treatment or presented in the literature (12). The doses tested in this study are within the dosing guidelines available in the literature (12). It is not expected for the study participant to experience any psychological harm during the study. Undesired changes in thought process and emotion may occur for the parents/legal guardians during the study. These changes are only expected to be transitory and not, recurrent or permanent.

2.3.3.3 *Invasion of Privacy*

The study does not involve any type of observation that would be seen as covert or intrusion.

2.3.3.4 *Social and Economic Harms*

The study does not involve any type of outcome that would be seen to affect the social or economic status of the parents/legal guardians or study participant.

2.3.3.5 *Minimization of Risk*

Minimization of risk will be achieved by following the listed guidelines:

- Study staff will receive complete information in the protocol regarding the experimental design and the scientific rationale underlying the proposed research, including the results of previous animal and human studies.
- A research team with sufficient expertise and experience to conduct the research will be assembled.
- Statisticians will ensure that the projected sample size is sufficient to yield useful results.
- As much data will be collected from standard-of-care procedures to avoid unnecessary risk, particularly for invasive or risky procedures (e.g., spinal taps, cardiac catheterization).
- Appropriate safeguards will be incorporated into the research design such as an appropriate data safety monitoring plan, the presence of trained personnel who can respond to emergencies, and procedures to protect the confidentiality of the data (e.g., encryption, codes, and passwords).
- The protocol has also been designed in order to meet the requirements of Part 46.205 (Protection of Human Subjects, Research involving neonates) which include:
 - Neonates of uncertain viability will not be included in the study

- Preclinical and clinical studies have been conducted and provide data for assessing potential risks to neonates
- Parents/Legal Guardians providing consent (in-person or remote) will be fully informed regarding the impact of the research on the neonate
- Study staff engaged in the protocol will have no part in determining the viability of a neonate

3 Objectives and Endpoints

3.1 Objectives

3.1.1 Primary Objective

The primary objective is to evaluate a potential dose-response of two different doses of intravenous phenobarbital for safety and efficacy in a neonatal population at high risk for seizures.

3.1.2 Secondary Objectives

- To assess the safety and tolerability of intravenous phenobarbital administration in neonates experiencing seizures.
- To assess the requirement of a second dose of intravenous phenobarbital in neonates with ongoing seizures.
- To assess the requirement of alternative anticonvulsive therapy in neonates with ongoing seizures.
- To characterize the seizure burden following administration of intravenous phenobarbital.

3.1.3 Exploratory Objectives

- To characterize the population pharmacokinetics of intravenous phenobarbital in neonates with seizures.
- To evaluate a potential dose-response of two different doses of intravenous phenobarbital for safety and efficacy in neonatal populations with different seizure etiologies.

3.2 Endpoints

3.2.1 Primary Endpoint

Percent of neonates who do not require additional seizure treatment after the first dose of phenobarbital during the first 24 hours after treatment.

Time zero (T0) will be defined as the start of the first loading dose 30-minute infusion.

3.2.1.1 Justification for Primary Endpoint

Primary endpoint is in line with recommendations provided by the US Food and Drug Administration. This measure should provide a clear delineation between the efficacy of the low and high loading doses of intravenous phenobarbital.

3.2.2 Secondary Endpoints

- Percent of neonates who do not require additional seizure treatment after 2 hours of the first dose of phenobarbital.
- Percent of neonates who do not require additional seizure treatment after the second dose of phenobarbital within the first 24 hours of treatment.
- Seizure burden over 24 hours following initial administration of the phenobarbital injection.
- Seizure burden over 48 hours following initial administration of the phenobarbital injection.
- Percent of neonates requiring alternative anticonvulsive therapy for the management of seizures at 24 and 48 hours.
- Time period between the first dose and second dose of intravenous phenobarbital in neonates randomized.
- Time period between the second dose of intravenous phenobarbital and alternative anticonvulsant treatment in neonates
- Time period between the first dose of intravenous phenobarbital and administration of an alternative anticonvulsant treatment in neonates randomized.

3.2.2.1 *Justification for Secondary Endpoints*

Reduction in seizure burden, seizure recurrence and administration of rescue ASDs have been identified as reliable outcomes to assess efficacy of antiepileptic drugs in late stage drug trials (22).

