4.1 Overall Design

This is a multicenter, randomized, double-blinded, active-controlled, parallel study in neonates (defined as ≥ 34 - ≤ 44 gestational weeks). The study will consist of a Screening Period, Double-Blind Treatment Period, Follow-up Period and an Open-Label Extension Period. The study participant population is neonates being admitted to the NICU and requiring continuous video electroencephalography (cvEEG) for seizure detection. One or two parents and/or legal guardians must provide written approval of informed consent, before the neonate can be assessed, monitored and managed in accordance with the study protocol and before any study data can be collected and recorded as study data. The reviewing IRB, based on its standard operating procedures, will determine number of parents/legal guardians who will be required to sign the informed consent.

Upon NICU admission and after parents or legal guardians provide informed consent, neonates will be monitored for electrographic seizures.

Seizures requiring study drug treatment will be defined as cumulative electrographic seizure of at least 30 sec/h (22). Confirmation of electrographic seizures by principal investigator or site designees (recommended to be a pediatric neurologist and/or neurophysiologist) is required. Randomization and study drug administration should start as soon as possible after the 30 sec/h of seizure activity criteria is met ideally within 30 min (maximum two hours) (22). If study drug cannot be administered within two hours of recognition of qualifying seizure burden (≥ 30 sec/h), then study drug should not be administered and the neonate will be discontinued from the study and will be a screen failure.

Following confirmation of seizure criteria, neonates will be randomized in a 1:1 allocation to receive a phenobarbital treatment loading dose of 20mg/kg or 40mg/kg, infused over 30 minutes.

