9.1 Statistical Hypothesis

This study was designed to show that high dose phenobarbital (40 mg/kg) is more effective than low dose phenobarbital (20 mg/kg) following single dose administration in terms of study's primary endpoint ([Section 3.2.1](#)). Specifically, the following primary statistical hypotheses will be tested.

Null hypothesis H_0 : there is no difference between treatments in the proportion of participants having a primary efficacy endpoint.

Alternative hypothesis H_a : The proportions of participants having a primary efficacy endpoint are different between the two treatment groups.

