9.2 Sample Size Determination

Literature supports that lower loading doses of phenobarbital achieve seizure control in approximately 30 to 60% of treated neonates, with higher loading doses achieving seizure control up to 85% (19, 20, 23, 24). Based on 70% and 50% of study participants achieving seizure control in high dose and low, respectively, an effect size of 20%, an alpha of 0.05 and 80% power, it is estimated that the number of completed study participants required will be 93 study participants in each group (total 186). With approximately, 5% dropout or unevaluable study participant, the minimum required for randomization will be 196.

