5.3. Planned Covariates

Covariate analyses will be performed on the primary outcome on the ITT population. The prespecified covariates in this study will be:

Stratification factors

- Presence or absence of HIE
- High or low seizure burden

Baseline values

- Gender (binary)
- Gestational age (continuous)
- birth weight (continuous)
- Apgar scores (continuous)
- Liver function tests (Total Protein, Albumin, Bilirubin, ALP, AST, ALT) (continuous)
- Seizure etiology (binary)
- pre-treatment seizure burden (continuous)

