7.2.2. Analysis of continuous outcomes

The continuous variables such as biochemical markers will be summarised using number of subjects (n), mean, standard deviation (SD), median (IQR), minimum, and maximum by treatment group, and will be analysed by a GLM model with treatment as a study variable, HIE (presence or absence) and seizure burden (high or low) as covariates, and with normal distribution and identity link function. Differences in mean outcomes with their two-sided 95% CIs between two groups will be derived from the GLM model.

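### SAP 7.2.2 adjusts the 24-h and 48-h seizure-burden endpoints only for HIE and a high/low burden flag, although continuous pre-treatment burden is already a planned covariate for the primary outcome; this gives up some precision

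*Protocol*

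**What the plan says.** Protocol 3.2.2 lists "Seizure burden over 24 hours following initial administration of the phenobarbital injection" as a secondary endpoint, with a matching one for 48 hours. Both are post-dose quantities with no baseline term. The justification in 3.2.2.1 is that "Reduction in seizure burden, seizure recurrence and administration of rescue ASDs have been identified as reliable outcomes to assess efficacy of antiepileptic drugs".

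SAP 7.2.2 analyses continuous outcomes by a normal GLM with identity link, with treatment and "HIE (presence or absence) and seizure burden (high or low) as covariates". Its example is biochemical markers. Seizure burden is not named, but no other SAP section covers continuous outcomes. SAP 5.3 calls the high/low burden variable a stratification factor, and neither document gives its cut-off.

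SAP 5.3 also lists "pre-treatment seizure burden (continuous") among the baseline values, but confines these covariate analyses to the primary outcome. Protocol 9.4.2 likewise uses pre-treatment burden in the adjusted analysis of the primary endpoint, and SAP 5.4 uses it, split at the median, as a subgroup. Protocol 9.4.3 says that secondary outcomes are handled similarly to the primary and names no covariates.

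**The concern.** Pre-treatment burden is the baseline measurement of the quantity that these two endpoints measure. The plan uses it in full to adjust a yes/no outcome, but reduces it to two levels when the outcome is burden itself. A two-level version of a continuous baseline explains less of the outcome's variance than the value does, so the confidence interval for the dose effect may be wider than the data require.

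Characterising seizure burden is a stated secondary objective. No power is given for these endpoints, and the trial was sized on a binary outcome. Precision that needs no extra neonates is therefore worth having if it can be prespecified.

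**Working it through.** **1. The plan's own figure.** The inputs from Protocol 9.2 are "Based on 70% and 50% of study participants achieving seizure control in high dose and low, respectively" and "an effect size of 20%, an alpha of 0.05 and 80% power". The test is two-sided, because the alternative in 9.1 is "The proportions of participants having a primary efficacy endpoint are different between the two treatment groups". Allocation is equal (Protocol 4.1: "neonates will be randomized in a 1:1 allocation to receive a phenobarbital treatment loading dose"). With pooled variance and no continuity correction:

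n per arm = [1.960 × √(2 × 0.6 × 0.4) + 0.842 × √(0.7 × 0.3 + 0.5 × 0.5)]² / 0.2² = 93

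This gives 186 completed, and 186 / 0.95 = 196 randomised. The stated figures reproduce. They concern the primary endpoint only.

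**2. Inputs for the burden endpoints.** The documents give no SD for burden and no correlation r between pre- and post-dose burden. I assume r = 0.2 to 0.7, SD 1, and a flag cut from the same pre-treatment value. HIE is in both models, so r is best read as the correlation left after HIE.

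**3. Formula.** For a normally distributed baseline:

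- residual variance with the continuous value: 1 − r²
- residual variance with the flag alone: 1 − f²r², where f = φ(z_p) / √(p(1 − p)) and p is the share of neonates on one side of the cut

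At a median split f² = 2/π = 0.637, so the flag keeps about 64% of what the continuous value explains. At 30/70 f² is 0.576, and at 20/80 it is 0.490. Under this model the flag adds nothing once the continuous value is included, so keeping both gives the same result apart from a degree of freedom.

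The variance ratio is (1 − r²) / (1 − f²r²). The confidence interval narrows by 1 − √ratio. The number completed for equal precision is 186 × ratio. Power is Φ(2.802 / √ratio − 1.960), for an effect fixed so that the flag-only model has 80% power at 93 per arm.

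**4. Results at a median split.**

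| r (assumed) | Flag only | Continuous | Ratio | CI narrower by | Completed N for equal precision | Power |
|---|---|---|---|---|---|---|
| 0.2 | 0.975 | 0.960 | 0.985 | 0.7% | 183 | 80.6% |
| 0.3 | 0.943 | 0.910 | 0.965 | 1.7% | 180 | 81.4% |
| 0.4 | 0.898 | 0.840 | 0.935 | 3.3% | 174 | 82.6% |
| 0.5 | 0.841 | 0.750 | 0.892 | 5.6% | 166 | 84.3% |
| 0.6 | 0.771 | 0.640 | 0.830 | 8.9% | 154 | 86.7% |
| 0.7 | 0.688 | 0.510 | 0.741 | 13.9% | 138 | 90.2% |

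With a 20/80 split the ratio runs from 0.979 (r = 0.2) to 0.671 (r = 0.7).

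**5. Skewed burden.** I simulated log-normal burden: 93 per arm, 4,000 trials per setting, log-SD 1.0 or 1.5, r defined on the log scale, and the flag replaced by the continuous value. The variance ratios were:

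| Outcome and covariate | r = 0.3 | r = 0.5 | r = 0.7 |
|---|---|---|---|
| Log outcome, log baseline | 0.96 | 0.88 to 0.90 | 0.73 to 0.75 |
| Raw outcome, raw baseline | 0.97 to 0.99 | 0.75 to 0.92 | 0.69 to 0.72 |
| Raw outcome, log baseline | 0.98 to 0.99 | 0.90 to 0.93 | 0.83 to 0.92 |

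On the log scale the closed form is confirmed. On raw minutes, which is what SAP 7.2.2 implies because it specifies no transformation, the ratio ranges from 0.69 to 0.99.

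**The case against.** The strongest reply is that nothing here is an error and the gain may be small. Most of that stands.

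- **Correlation.** There are reasons to expect a weak link. The outcome covers 24 to 48 hours after active treatment, control is assumed in 50% to 70% of neonates, and persisting seizures lead to a second dose or another anticonvulsant. At r of 0.2 to 0.3 the interval narrows by less than 2%.
- **Partial adjustment already exists.** The flag recovers roughly half to two-thirds of what a normally distributed baseline would explain. SAP 6.2 also allows imbalances judged clinically relevant to be examined in an exploratory way. That is discretionary, however, and does not put the covariate in the model.
- **The word similarly in Protocol 9.4.3.** It could be read as carrying over the covariate-adjusted model of 9.4.2. SAP 5.3 and 7.2.2 do not carry it over.
- **Availability.** A full recorded hour before T0 is not assured. Recording starts at consent or hook-up, whichever is later. The entry criterion is 30 cumulative seconds of seizure in an hour, and Protocol 4.1 wants dosing ideally within 30 minutes of meeting it. Protocol 8.1.1.1 asks for the times of every seizure in the CRF, but the list in 8.1.4 starts at the first dose. The whole EEG is archived, but the protocol specifies no later reading step.
- **A prior question.** After the first 2 hours, 8.1.4 lists only seizures that prompted treatment. Unless this is reconciled with 8.1.1.1, the 24-h and 48-h outcomes themselves are uncertain, which matters more than a covariate.

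A reader might also infer from 3.2.2.1 that the protocol promises a change from baseline and that the endpoints break the promise. The text does not say so. It names reduction in burden as a class of outcome, and in a randomised trial comparing post-dose burden between arms estimates the dose effect on burden.

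**Conclusion.** The point holds as a question of efficiency. The SAP models for 24-h and 48-h burden leave out a continuous baseline value that the sponsor already plans to derive. With a median-split flag, the variance of the dose effect would fall by about 1.5% at r = 0.2, 11% at r = 0.5 and 26% at r = 0.7, and the interval would narrow by 0.7%, 5.6% and 14%. The gain is material only from about r = 0.5.

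These figures rest on an assumed correlation, an assumed cut-off for the flag, and a scale on which the baseline relates roughly linearly to the outcome. On raw minutes the gain may nearly vanish.

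A reader might go further and conclude that the dose comparison is biased, or that a chance imbalance in severity invalidates it. Neither follows: randomisation protects the estimate, and its confidence interval already reflects chance imbalance. The endpoints are secondary and treated as exploratory (SAP 5.6). The primary analysis and its sample size are not affected.

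**What to change.** In SAP 7.2.2:

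1. Name the 24-h and 48-h seizure-burden endpoints explicitly.
2. For these two models, add continuous pre-treatment burden as a covariate alongside HIE and the high/low flag.
3. Put covariate and outcome on the same scale. A log-type scale suits skewed burden, and it must allow for zero post-dose burden.
4. Define pre-treatment burden as minutes of seizure per recorded hour over the cvEEG available before T0. A rate is needed because recorded time before T0 differs between neonates (screening may last up to 24 hours), and a fixed full hour may not exist.

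Reconcile Protocol 8.1.1.1 with 8.1.4 so that pre-dose seizure times are captured. The same edit should settle how seizures after the first 2 hours are recorded.

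The cost is small: one covariate in two secondary models, a defined baseline window, and entry of pre-dose seizure times. The covariate analysis already planned for the primary outcome needs the last two anyway. On a log-type scale the estimated effect is no longer a difference in mean minutes, so the report should say how it is to be read.
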